Following consultation with our Patient and Public Intervention (PPI) group, we will ask a bespoke question about participants' perception of their ability to cope with life on a 5-point Likert scale.

Parent-Adolescent Relationship Scale PARS; (Burke et al., 2021).

Critical Dimensions of the parent–adolescent relationship will be assessed from multiple perspective using the Parent Adolescent Relationship Scale (Burke et al., 2021). The PARS is a 20-item measure that comprises three subscales: connectedness, shared activities, and hostility. Initial research has demonstrated good discriminant and convergent validity (Burke et al., 2021).

Mediators

Collected at T0, T1, T2:

PARS (Burke et al., 2021) (above) is also a mediator.

CHIME-S (Karl et al., 2024)/CHIME A (C. Johnson et al., 2017)

The Comprehensive Inventory of Mindfulness Experiences CHIME; (Karl et al., 2024) is an established selfreport questionnaires available in parallel versions for adults (Bergomi et al., 2014; S. Wilkinson et al., 2023) and adolescents (C. Johnson et al., 2017). The CHIME-S and CHIME-A cover mindfulness as a complex construct consisting of the following facets (subscales):

• Awareness of Internal Experience,

- Awareness of External Experience,
- Acting with Awareness,
- Accepting and Nonjudgmental Orientation,
- Decentring and Nonreactivity,
- Openness to Experience,
- Relativity of Thoughts, and
- Insightful Understanding.

They will be administered at all main trial assessment points for all individuals, young people, and carers.

Self-Compassion Scale Short Form SCS-SF; (Raes et al., 2011)

The SCS-SF (Neff, 2016; Raes et al., 2011) is a 12 item self-report measure of self-compassionate responding in the event of failure and distress. Items are rated on a five-point scale from 1 (almost never) to 5 (almost always). The measure has excellent internal consistency (α = .89) as well as good convergent, divergent, content and face validity (Raes et al., 2011).

Emotion Regulation Questionnaire ERQ; (Gross & John, 2003)

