Following written consent, participants will be randomised in a 1:1 ratio to one of the two treatment arms (TAU, or MAC + TAU). A web-based randomisation system will be designed, using the bespoke KCTU randomisation system. The randomisation system will be created in collaboration with the trial analyst/s and the CI and maintained by the King's Clinical Trials Unit for the duration of the project. It will be hosted on a dedicated server within KCL. The system will employ block randomisation with randomly varying block sizes and will be stratified by i) site, ii) if the young person is taking a therapeutic dose of antidepressants or not and iii) if their RCADS (Ebesutani et al., 2012) score at baseline indicates that they have severe depression or not. The details needed for randomisation will be held in a dedicated database. Only the Programme Manager, Trial Manager and Programme Administrators (unblinded) will have access to the randomisation system (or their nominated backup in times of absence; the nominated backup will not be another member of the blinded team but will be a team member whose role on the delegation log specifies this role as contingency Trial Manager).

Sample size calculation

Our power calculation suggests that 480 participants (240 per arm, MAC allocation=20 groups) will allow us to detect an effect size of 0.3 with 90% power, allowing for 20% attrition. The calculation assumed using a two-sided independent samples t-test of the difference between arms, alpha = 0.05, assuming a MAC group size of 12, intraclass cluster correlation of 0.05, i.e. a design effect / inflation of $1 + [12 - 1] \times 0.05 = 1.55$ (Williams et al., 2008), one baseline and two post-randomisation measures with correlation rho = 0.5 = deflation factor of 0.5 (Machin et al., 2009), and 20% attrition (Kennard et al., 2009;(Mental Health Taskforce, 2016). The calculation was done using the Gpower software, with methods from Killip et al used to hand-calculate the cluster effect for MAC group (Killip, 2004).

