17. MEDIATION ANALYSIS

Decentring

To investigate the purported core mechanisms of the treatment, we will test whether treatment-related changes on the Decentring and Nonreactivity scale of the CHIME/CHIME-A questionnaire mediate change in depressive symptoms in both young people and carers.

Mindfulness skills

To investigate the role of general mindfulness skills, we will investigate whether treatment-related increases in mindfulness skills across all facets of the CHIME/CHIME-A mediate levels of depressive symptoms (i.e., total CHIME/CHIME-A scores across all subscales). To explore the relative contributions of treatment-related changes in mindfulness facets (all the CHIME/CHIME-A subscales) to the mediation of the primary treatment outcome, we will run multiple parallel mediator models using a stepwise approach to enter the different subscales to identify the most relevant facets in both groups, as shown in **Figure 6**.

Figure 6: Graphical representation of mediator models used to investigate the role of general mindfulness skills

Self-compassion

While not explicitly listed in our logic model, we will also investigate potential mediating effects of selfcompassion, a characteristic that is integral to the attitudinal components of mindfulness and has previously been shown to increase following MBIs.

Sequential mediation pathways

Including cognitive targets of decentring and mindfulness skills: To better understand how increases in decentring and general mindfulness skills may impact on symptoms, we will explore pathways in a more comprehensive model that includes cognitive target variables, separately in young people and in adults. Based on previous research, this model assumes that decentring is particularly suited for reducing ruminative tendencies (Wu et al., 2022; Ishikawa et al., 2018), while general mindfulness skills not only support the ability to decentre but benefit emotion regulation more widely (Desrosiers et al., 2014). That is, we assume two separate sequential pathways, one in which decentring reduces rumination thereby reducing symptoms and another in which mindfulness increases emotion regulation skills thereby reducing symptoms, as shown in **Figure 7**.

Figure 7: Graphical representation of sequential mediation models used to investigate the role of decentring and general mindfulness skills

Transfer across the young person-carer dyad

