We will test, in young people and in parent/carers, whether the degree to which they engage in practice during the intervention is related to changes in decentring and mindfulness skills over the period of the intervention, and to levels of symptoms measured using the SMFQ. We assume that regular practice is necessary for effective development of the treatment-related skills that serve to reduce depression and will test the hypothesis that effects of practice on depressive symptoms during follow-up are mediated through changes in decentring and general mindfulness skills during the intervention, both in young people and in adults who participated in MAC. We will use similar methods to those described above for the other mediation modelling, but will just model data from the individuals in the MAC arm, i.e., those for whom we can measure engagement in practice.

Mediation analysis methods

Mediation will be evaluated using structural equation modelling and/or causal mediation analysis methods adjusting for the stratification variables and baseline measures where appropriate (i.e., adjusting for baseline measures of mediator and outcome in mediator models (Dunn et al., 2015) and using appropriate modelling methods (i.e., temporally ordered mediator and outcome, longitudinal models where appropriate). Given previous research on MBCT that has provided evidence for the importance of acquisition of therapy-related skills across the intervention period (C. Crane et al., 2014), as well as their refinement and continued utilisation after the end of the intervention (Segal et al., 2019), we will run separate sets of analyses to test mediation of outcome at the end of intervention and at the end of follow-up. We may explore the extension of this methodology to repeated measures/AUC models. If we find significant baseline moderators of treatment effect, we may explore whether there is mediated moderation (Dunn et al., 2015; Muller et al., 2005). All mediation models will use raw mediator and outcome scores adjusted for baseline scores, rather than change scores (Landau et al., 2018).

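### Stepwise selection among eight CHIME facets makes ordinary estimates and intervals for the retained facets invalid; one model holding all eight would avoid this

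*Protocol*

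**What the plan says.** Protocol section 17, under Mindfulness skills, first tests mediation through the CHIME/CHIME-A total score. It then turns to the separate facets. The purpose is worded "To explore the relative contributions of treatment-related changes in mindfulness facets", and the method is multiple parallel mediator models "using a stepwise approach to enter the different subscales to identify the most relevant facets in both groups". The two groups are young people and carers.

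Section 14, under Mediators, lists eight facets, from Awareness of Internal Experience to Insightful Understanding. Section 17, under Mediation analysis methods, adds: "we will run separate sets of analyses to test mediation of outcome at the end of intervention and at the end of follow-up". On inference it says: "Mediation will be evaluated using structural equation modelling and/or causal mediation analysis methods adjusting for the stratification variables and baseline measures where appropriate".

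For the facet step the protocol states no entry or removal criterion, no resampling or validation, and no adjustment for selection or multiplicity. Two other mediator tests in section 17 use scores fixed in advance: the Decentring and Nonreactivity subscale, named as the core mechanism, and the CHIME total.

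**The concern.** A standard error, interval or p-value from a mediator model is derived for a model chosen before the data were seen. Here the data choose the model, and a facet stays in because its coefficient looked large. The retained coefficients are therefore biased away from zero and their intervals are too optimistic. That damages the quantity the step is meant to deliver, the relative contribution of each facet. The facets are also correlated parts of one questionnaire, so which of them enters first can turn on chance.

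At stake is the statement of which parts of mindfulness carry MAC's effect. That statement feeds the protocol's research question on the exact pathways (section 9, question 5).

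**Working it through.** **1. The plan's own figures.** The protocol gives no error rate for the facet step. The nearest figure is the sample size: "480 participants (240 per arm, MAC allocation=20 groups) will allow us to detect an effect size of 0.3 with 90% power, allowing for 20% attrition", from a "two-sided independent samples t-test of the difference between arms, alpha = 0.05". For an effect of 0.3 the unadjusted size is 234 per arm (235 by t-test). The design effect is 1 + 11 × 0.05 = 1.55. The repeated-measures factor is (1 + 0.5)/2 − 0.5² = 0.5. So 234 × 1.55 × 0.5 / 0.8 = 226.7, or 227 per arm (228 from 235), 454-456 in total. The planned 480 is 20 groups of 12 plus an equal TAU arm. It gives 240 × 0.8 / (1.55 × 0.5) = 247.7 effective per arm and 91.6% power. The figure stands, slightly on the safe side. For the mediation models it implies n = 480 × 0.8 = 384 after attrition; 300 is an assumed lower value.

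**2. Size of the search.** Eight facets, in 2 groups × 2 end points = up to 4 searches. For eight independent tests at 0.05 the chance of at least one false positive is 1 − 0.95⁸ = 33.7%.

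**3. Simulation set-up.** The protocol supplies only the eight facets and the n above. The following are assumptions:
- facets equally correlated at 0.4;
- forward entry on the facet-to-outcome path at p<0.05, conditional on arm;
- a facet is declared a mediator if both its arm-to-facet path (a) and its facet-to-outcome path (b) have p<0.05 (joint significance).

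Runs were 400 to 2,000 per setting. At 400 runs a rate of 25% has a Monte Carlo standard error of √(0.25 × 0.75 / 400) = 2.2 points.

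**4. Harm from selection itself.** Three facets truly mediate, at 0.15 per SD each.
- Coverage of nominal 95% intervals for retained facet-to-outcome effects: 78-84%. With all eight facets entered: 94-96%.
- Mean excess of retained coefficients over their true values: 0.04-0.06 per SD. For scale, 0.04/0.15 = 27% and 0.06/0.15 = 40% of the effect assumed for a true facet.
- If no facet affects symptoms, the intervals of retained facets covered zero in 0% of cases, because entry itself required p<0.05.

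**5. False mediators, one group at one end point.** Chance of declaring at least one when none mediates:

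| Null setting | n | Stepwise | Eight fixed, uncorrected | Eight fixed, 0.05/8 |
|---|---|---|---|---|
| a = 0.5, b = 0 | 300 | 27% | 34% | 4% |
| a = 0.5, b = 0 | 384 | 26-30% | 31% | 4% |
| a = 0, b = 0.12 | 300 | 16-17% | 14% | 1% |
| a = 0, b = 0.12 | 384 | 19-23% | 20% | 1% |
| a = 0, b = 0.20 | 300 | 23-24% | 22% | 3% |
| a = 0, b = 0.20 | 384 | 25-26% | 25% | 3% |
| a = 0, b = 0 | 300 / 384 | 2.1% / 0.8% | – | – |

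Ranges show repeat runs. A further repeat of 400 runs gave 17-29% for stepwise and 12-37% for the uncorrected fixed model; corrected rates in repeat runs were 1-6%. Stepwise and the uncorrected fixed model differ little. The drop comes from the 0.05/8 threshold.

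**6. Dependence on the assumptions** (n = 384, no clustering or baseline covariates). With a = 0.3 and b = 0, stepwise gives about 28% at facet correlation 0 and 15-16% at 0.7. One facet named in advance gives 4-5%. A looser entry rule (p<0.157) gives 30-37%. A Sobel test gives 7-10%, and Monte Carlo product intervals give 14-26%. Over all null settings tried, the range is about 1% to 37%.

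**The case against.** Four points can be made for the plan.

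- **It is exploratory and the SAP may handle it.** The step is worded as exploration, section 16 leaves detail to the SAP, and multiplicity in a mechanism analysis is commonly settled there. This stands in part: the absence of a multiplicity rule in the protocol would not be a finding alone. But stepwise entry is a stated choice, and an SAP that follows the protocol inherits it. Exploratory wording does not repair biased estimates.
- **Stepwise entry is not the main source of false positives.** This stands. A reader might infer that fixing the model would bring the rate down; the table shows that without correction it does not.
- **The rate is conditional.** This also stands. A reader might take 16-30% to apply whenever no facet mediates. It applies when MAC moves the facets but they do not affect symptoms, or the reverse, under an entry rule and test that the protocol does not specify.
- **The replacement does not find the true set more often.** Correct. With three true mediators, stepwise returned exactly those three in about 10-24% of runs, and the Holm-adjusted model in only 1-5%. Poor recovery of the true set is no argument against stepwise entry here.

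A reader might also infer that survivors will be published as established mediators with unadjusted p-values. The protocol does not say so.

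**Conclusion.** The concern holds in a limited form. The protocol commits to data-driven selection among eight facets, in two groups and at two end points, and states no allowance for it. Ordinary estimates and intervals for the retained facets are then invalid: about 78-84% coverage against a nominal 95%, and effects too large by about 0.04-0.06 per SD.

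The excess of false mediators, about 16-30% per search when only one path exists and about 2% when neither does, is a separate problem. It is mainly uncorrected multiplicity. More than one search would raise the overall chance.

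All of these sizes rest on assumed facet correlation, path sizes, entry rule and mediation test; the direction of the selection bias does not depend on the exact values. The point is confined to the exploratory facet step. The decentring test, the CHIME-total test, the primary outcome and the sample size are unaffected.

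**What to change.** In section 17, under Mindfulness skills, replace the stepwise entry with one prespecified parallel-mediator model per group and end point that contains all eight subscales. Report the total indirect effect and all eight facet-specific indirect effects, with intervals and Holm-adjusted p-values, labelled exploratory. Both parts are needed: the full model removes the selection bias, and the adjustment deals with the multiplicity. If a short list is still wanted, bootstrap the whole selection procedure and report how often each facet is selected, without post-selection p-values.

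The cost is wording in the protocol and SAP, with no new data or participants. The price is wider facet-level intervals, because the subscales are correlated, and lower facet-level power. In simulation, power at n = 300 was 87% for a single facet of 0.3 per SD; smaller effects will often be missed.

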18. HEALTH ECONOMIC ANALYSIS

Our economic analysis will evaluate the cost and cost-effectiveness of MAC plus TAU compared to TAU alone from NHS/personal social services, education, and societal perspectives. To do this we will:

- Undertake a detailed analysis of the costs of MAC,
- Evaluate the within-trial impact of MAC on
 - Resource use and costs,

- Health-related quality of life,
- Quality-adjusted life-expectancy,
- Model the long-term impact of depression in childhood on a range of outcomes using longitudinal datasets,
- Evaluate the cost-effectiveness of the intervention in the short-term and long-term from
 - o NHS,
 - o Education,
 - Personal social services,
 - Societal perspectives.

An economic analysis is warranted given the non-zero cost of MAC and its potential impact on depression and associated costs. Our analysis will conform to accepted economic evaluation methods (National Institute for Health and Care Excellence (NICE); (NICE Health Technology Evaluations: The Manual NICE Process and Methods, 2022). We will estimate costs and cost-effectiveness for the 'within-trial' period, and, using modelling, over a lifetime time horizon. Costs will be assessed from the perspective of the NHS and personal social services (PSS; base case analysis), and also from a wider societal perspective (secondary analysis). A Health Economic Analysis Plan will be presented to the Trial Steering Committee for approval before data lock and prior to any analysis being undertaken.

The resource use data collected in the trial will be valued using UK unit costs (in $2022/2023 \pm$). Unit costs will be identified from published sources, including the:

- British National Formulary (https://bnf.nice.org.uk/),
- Unit Costs of Health and Social Care (https://www.pssru.ac.uk/project-pages/unit-costs/),
- Prescription Cost Analysis (https://www.nhsbsa.nhs.uk/prescription-data/dispensing-data/prescription-cost-analysis-pca-data), and
- National Schedule of NHS Costs (https://www.england.nhs.uk/national-cost-collection/).

Health Economic outcome measures

- Quality-adjusted life years (QALYs) accrued by participants (QALYs are the recommended outcomes for economic evaluations in the UK (NICE Health Technology Evaluations: The Manual NICE Process and Methods, 2022),
- The trial primary outcome (SMFQ-measured depression),
- Other trial secondary outcome measures including those for parents and carers.

QALYs will be calculated based on the following collected during the trial:

- Health-related quality of life (HRQL) data, and
- Mortality data.

HRQL will be measured using the EQ-5D-5L, which we will collect for a 12-month period at baseline (randomisation) and 14 weeks- and 12-months post-randomisation for each individual participant. This period will cover the period during which the MAC sessions occur, and time thereafter.

Utility scores will be computed from the EQ-5D-5L descriptive system data using recommended algorithms for the UK population at the time of analysis. Participant-specific utility profiles will be constructed assuming a straight-line relation between each of the participant's EQ-5D-5L utility scores at each of the three follow-up points. If any participants die within the 12-month period, they will be assigned a utility score of zero at the date of death and thereafter. The QALYs experienced by each participant from baseline to 12 months will

be calculated as the area underneath the utility profile. Unit costs will be taken from standard published sources.

The cost-effectiveness measures in the within-trial (12-month) model will be the:

- Incremental cost per case of SMFQ-measured depression avoided (cost-effectiveness analysis, CEA),
- Incremental cost per quality-adjusted life year (QALY) gained (cost-utility analysis, CUA), and
- Cost consequences analysis (CCA) presenting the costs associated with the intervention and the full range of trial secondary outcome measures.

This analysis will be closely aligned with the analysis of effectiveness in the main trial in WP3. Multiple imputation by chained equations will be used to deal with missing EQ-5D-5L and resource use values (Faria et al., 2014). Subsequent analyses of imputed data will include variance correction factors to account for additional variability introduced into parameter values as a result of the imputation process (Little & Rubin, 2014). In the CEA and CUA, cost-effectiveness will be calculated as the mean cost difference between the intervention versus control, divided by the mean difference in outcomes (SMFQ-measured depression, QALYs) to give incremental cost-effectiveness ratios (ICERs). In the CUA we will also calculate costeffectiveness measures based on net monetary benefits and incremental net monetary benefits (iNMBs). Non-parametric methods for calculating confidence intervals around the ICER and iNMB based on bootstrapped estimates of the mean cost and QALY differences will be used (A. H. Briggs et al., 1997). The bootstrap replications will also be used to construct a cost-effectiveness acceptability curve, which will show the probability that MAC is cost-effective at 12 months for different values of the NHS' willingness to pay for an additional QALY. We will subject the results to extensive deterministic (one-, two- and multi-way) sensitivity analysis. We will also undertake separate cost-effectiveness calculations for pre-specified subgroups of the trial population, as defined in the main trial statistical analysis plan. Theoretical and empirically derived subgroups include the include severity of depression and/or comorbid anxiety at baseline, exposure to childhood trauma, ethnicity, and age group (15 to 16 versus 17 to 18).

Lifetime cost-effectiveness of MAC

These will be calculated in terms of the incremental cost per QALY gained (lifetime CUA) and longer-term costs and spill-over effects associated with childhood depression, measured in terms of health, lifestyles and behaviours, educational attainment, employment, earnings (lifetime CCA). We will construct a de novo cost-effectiveness model, since reviews of economic evidence suggest that no long-term economic models of the management of depression in children exist (*NG134 2019 Evidence Review A*, 2019b). Assuming this remains the case at the time of analysis, we will model long-term costs and outcomes associated with depression in childhood using UK longitudinal datasets (e.g., National Child Development Study, NCDS, English Longitudinal Study of Aging, ELSA, Avon Longitudinal Study of Parents and Children, ALSPAC) coupled with secondary cost and HRQL evidence from published sources. This will replicate an approach that we have used previously to model the long-term costs and consequences of child maltreatment from health and societal perspectives (Conti et al., 2021). We will use regression analysis to predict longitudinal outcomes of measures of depression in childhood available in NCDS, ELSA and ALSPAC. The outcomes we select to model will be identified from a scoping review of reviews of the literature but are likely to include relapses of depression at older ages, and impacts on:

- Anxiety,
- Other mental health problems,
- Smoking,
- Alcohol abuse,

- Educational attainment,
- Marital status,
- Labour market outcomes (employment and earnings) and
- Welfare services use.

This analysis will allow us to predict the impact of childhood depression on the incremental probability of each outcome at the different ages used as follow-up points in the longitudinal studies. We will linearly interpolate the probabilities between these ages to produce tables of risk probabilities for every outcome for all ages across the life course. Annual costs for each outcome will be obtained, identifying published cost estimates from previous UK cost or cost of illness studies where possible, from searches of the literature, including:

- PubMed,
- NHS Economic Evaluations Database,
- EconLit and
- Google Scholar.

HRQL impacts associated with each outcome, and by age group where possible, will be obtained from a review of utilities from the CEA Registry Database at Tufts University (CEA Registry Database at Tufts University https://cevr.tuftsmedicalcenter.org/databases/cea-registry).

This analysis will result in estimates of the lifetime cost and QALY impacts of depression in childhood; these will be incorporated into the economic modelling based on differences in depression found in the trial (SMFQ-measured depression, the primary outcome). We will undertake deterministic (one-, two- and multi-way) and probabilistic sensitivity analysis, the latter assuming appropriate distributions and parameter values (A. Briggs et al., 2006).

In addition, we will combine data on incremental costs with epidemiological data on projected numbers and undertake a budget impact analysis to evaluate what the total cost impact of rolling out the use of the MAC intervention were it to be scaled up. We will use the probabilistic sensitivity analyses to undertake a value of information analysis (A. Briggs et al., 2006) to evaluate the potential economic value of future research on the use of MAC. We will discuss how best to utilise and present the findings of the economic analysis in WP5 to inform implementation of the MAC intervention.

